***Medical or professional intervention in the event of adverse effects to the subjects.***

All research performed under this study will conform to laws, regulations policies and procedures pertaining to protections for human subjects. Collaborating centers and the Coordinating Center shall immediately notify each other, and the investigator shall promptly notify the IRB, upon identifying any aspect of the Protocol, including unanticipated problems involving risk and information discovered during site monitoring visits/remote site monitoring visits or in the study results that may adversely affect the safety, well-being, or medical care of subjects, or that may affect the willingness of subjects to continue participation in the research, may influence the conduct of the study, or may alter the IRB's approval to continue the study. When subject safety could be directly affected by study results, the Coordinating Center will notify participating sites who will provide written communication to affected subjects.

The Investigator and/or research coordinator at each participating center will be responsible for collecting data in regard to adverse events. The investigator must decide whether each incident meets the definition of a SAE. Once the local Principal Investigator (PI) determines that a serious adverse event meets reporting requirements, he/she must report the SAE, and related safety information, to the Coordinating Center on the required *Significant Adverse Event Report Form* (See form attached) provided for this purpose. Additionally, local SAEs should be reported to the Coordinating Center and IRB of record per policy. If the adverse event results in the need to revise the informed consent, or other study documents, the PI will submit a request for a modification through the Coordinating Center to the IRB of record. An extensive Data Safety Monitoring Plan (DSMP) is provided.

**Potential Benefits of the Proposed Research to Human Subjects and Others**

The prevalence of frequent/high PVC burden and cardiomyopathy is key as it is likely that subjects are under recognized. Furthermore, understanding the potential benefits of RFA of PVCs versus AAD therapy in subjects with CM and frequent PVCs are particularly important to subjects as we will try to understand the best treatment strategy to eliminate PVCs and if indeed both improve LV function, change quality of life, improve or even eliminate HF symptoms, morbidity and mortality, as well as avoid the need for implantable cardiac devices with all associated medical expenses. In addition, understanding the PVC features associated with CM is paramount to properly target subjects that are likely to respond to RFA of PVCs, and avoid this invasive procedure in subjects that are less likely or do not have clinical benefit.

***Risks versus anticipated benefits to research participants and others.***

The risks of the subjects participating in this research proposal are reasonable, since it is not clear if the benefits outweigh the risks of RFA. Even though risks of RFA are considered small, these can be serious (cardiac tamponade, bleeding, stroke, AV block, myocardial infarction) and even result in death. Current clinical practice offers RFA to subjects with frequent PVCs associated with cardiomyopathy supported only on retrospective and non-randomized observational studies with a relatively short 3-6 month follow up period. It is unclear if PVCs would decrease with time and without intervention with subsequent improvement of LV function without the need for invasive procedures. Thus, we believe that we need to further study the benefits of this invasive procedure to assure that it justifies the risks associated with it.

**Importance of the Knowledge to be gained**

**Discuss the importance of the knowledge gained or to be gained as a result of the proposed research.**

The PAPS pilot study will help us understand the prevalence of PVC-CM and gather key information to better design and power a large randomized trial – the PAPS study. This large randomized study would aim to improve evidence-based treatment options in subjects with frequent PVCs and LV dysfunction with or without heart failure, as we plan to compare RFA of PVCs vs. antiarrhythmic drug (AAD) therapy.

Subject's health could be improved in those subjects with PVC-CM if subsequent normalization of LV function occurs after RFA of PVCs, avoiding heart failure and device implantation. Otherwise, these

subjects can be incorrectly considered or diagnosed with a persistent irreversible form of CM with subsequent HF morbidity and mortality. Thus, subjects with PVC-CM could have a significant improvement and/or normalization of quality of life, heart failure symptoms and NYHA class, while decreasing morbidity and mortality associated with HF and CM after elimination of PVCs with RFA. Moreover, these subjects would not require implantable cardiac devices.

Change in current clinical practice would occur if our study's hypotheses are proven correct, since Holter monitors would be routinely requested as standard of care to rule out PVC-CM in all the following subjects: 1) newly diagnosed CM with or without heart failure and 2) chronic LV dysfunction that demonstrate PVCs with or without heart failure and/or implantable cardiac devices. Furthermore, this study would attempt to understand predisposing factors and PVC features associated with PVC-cardiomyopathy. This would lead to a change in current practice as it will guide us to closely follow up those subjects at risk to develop PVC-CM.

The proposed study will impact several aspects of subject care, such as: 1) evaluate clinical benefits of RFA of PVC in subjects with suspected PVC-CM, by assessing changes in quality of life, HF symptoms and morbidity, 2) assess improvement in LV function after RFA of PVCs and/or AADs, which will in turn reduce the need for expensive implantable cardiac defibrillators (ICDs); 3) identify the PVC burden threshold required to induce CM, helping us to properly diagnose PVC-CM and target specific therapy, such as RFA of PVCs, to only those subjects likely to respond to RFA; and 4) decrease the financial burden associated with poor quality of life, heart failure symptoms and hospital admissions, and ICDs in subjects with frequent PVCs and CM.

#### Risks to subjects in relation to the importance of the knowledge that may be expected to result.

Risks associated with research subjects in this proposed study are considered small and acceptable since most of these subjects would have been scheduled for RFA of PVCs without a clear understanding of the benefits associated with RFA. In contrast, the risks related to those subjects undergoing RFA of PVCs are small but can be potentially severe (as described above).

Current gaps in knowledge include: 1) possible placebo effect of RFA as spontaneous resolution of PVCs could have occurred even without RFA of PVCs, 2) best treatment strategies, either RFA or AADs, to achieve successful PVC suppression, 3) unclear clinical benefits (quality of life, NYHA class, HF symptoms, HF morbidity and mortality, implantable cardiac devices) of RFA of PVCs or AADs in the setting of PVC-CM, and 4) PVC features required to induce CM, in which subjects should be referred to RFA of PVCs or initiate AADs. Until now, there have been no randomized-controlled studies of subjects with PVC-CM to clarify and answer these questions.

*In summary, without clear evidence of the benefit of RFA in subjects with cardiomyopathy associated with frequent PVCs, we believe that the risk of withholding RFA is similar to the risk of those subjects undergoing an invasive procedure such as RFA of PVCs.*

#### **Data and Safety Monitoring Plan (DSMP)**

A detailed Data and Safety Monitoring Plan (DSMP) will be submitted to the IRB and NIH (funding institution) for approval prior to the accrual of human subjects. The Data Safety Monitoring Plan is written to ensure the safety of the participants and verifying the validity and integrity of the data (see details in document: Protection of Human Subjects). Details are expanded on document: Data Safety Monitoring Plan.

A Data and Safety Monitor Board (DSMB) will consist of 2 heart failure specialists (Drs. [name] and [name]) and a cardiac electrophysiologist ([name]) (see letters of support) that have no direct investment in the study to prevent jeopardizing subject safety. In addition to the Coordinating Center and central IRB, the DSMB will review the research protocol and plans for data safety and monitoring, evaluate the progress of the trial with periodic assessments of data quality and timeliness, participant recruitment, accrual and retention, participant risk versus benefit, and reports from related studies.

The DSMB will meet every 4 months to review data and adverse event reports. Additionally, they will meet to review interim analysis when available. This will be performed in a closed session with open access to the PI if requested by the Board. Data monitoring will focus on several areas: 1) Performance, which will allow us to assess site performance with respect to subject recruitment, retention and follow-up, flow of data forms, protocol adherence and quality of data; 2) Safety, which will allow us to assess the magnitude

of adverse events; and 3) Treatment, in order to monitor and assess treatment effects (described under Section: Potential Risks).

### **ClinicalTrials.gov Requirements**

As required, the PAPS pilot study has been registered at [www.clinicaltrials.gov](http://www.clinicaltrials.gov) (NCT03228823).  
<https://clinicaltrials.gov/ct2/show/NCT03228823?term=NCT03228823>

### **Inclusion of Women, minorities and children**

As per instructions, these aspects are detailed in separate documents:

- 1) Inclusion of Women and Minorities.
- 2) Inclusion of Children.

---

## DATA SAFETY MONITORING PLAN

---

The PAPS Pilot study is a national multicenter randomized control study to enroll between 36-39 subjects with cardiomyopathy associated with frequent PVCs. This is a phase IV trial with moderate risk as participating subjects will be randomized to two different strategies (RFA versus AAD) commonly used in clinical practice to treat subjects with frequent PVCs. We consider this study to be moderate risk since most subjects with a suspected PVC-CM would undergo RFA as a common clinical practice (as discussed above). All research performed under this study will conform to laws, regulations and VA policies and procedures pertaining to protections for human subjects.

In addition to Coordinating Center and central IRB oversight, a Data Safety Monitoring Board (DSMB) will be organized according to the FDA recommendations to review all serious adverse events as well as study progress (including all adverse events) every 4 months after study initiation. The DSMB will be integrated by faculty members from institutions without active enrollment in the study and without a vested interest in the proposed research that have different expertise (see DSMB section in Protection of Human Subjects document). The members of the DSMB will have full access to all study records and will have the authority to discontinue the study at any time. Please consult the Protocol in Appendix for additional details.

A detailed Data and Safety Monitoring Plan (DSMP) will be submitted to the IRB and NIH (funding institution) for approval prior to the accrual of human subjects. The Data Safety Monitoring Plan is written to ensure the safety of the participants and verifying the validity and integrity of the data.

During each scheduled visit and in between visits, subjects will be asked and instructed to call in regard to any event out of the ordinary. Those subjects randomized to the RFA group will be evaluated immediately, throughout the first 24 hours and 1-2 weeks after the procedure by the research team as standard follow up on any of these procedures. It will be the responsibility of the investigator/coordinator to assess the subject personally and request laboratory or any appropriate tests if needed. All adverse events including serious adverse events (SAE) will be monitored for all subjects during their participation in this study.

a. Adverse event (AE) grading and attribution scale. The investigator will try to determine the relationship of adverse event to RFA and/or AAD therapy as not related, possibly related, or definitely related using standard criteria for clinical trials. All grades of toxicity will be noted.

The following grading and attribution scale will be employed:

- 0 = No adverse event or within normal limits
- 1 = Mild AE, not requiring treatment
- 2 = Moderate AE, resolved with treatment
- 3 = Severe adverse event (SAE) is any untoward medical occurrence that at any point during the study:
  - Results in death
  - Life-threatening – refers to an event in which the subject was at risk of death at the time of the event; it does not refer to an event which hypothetically might have caused death if it were more severe.
  - Requires in-patient hospitalization or prolongation of existing hospitalization – Hospital admission is usually interpreted as requirement of at least one overnight stay in subjects in the medical therapy arm or PVC suppression; whereas in subjects in the PVC suppression arm, a prolonged hospital stay will be defined if more than two days of hospital stay is required after RFA ablation. Treatment and release from an emergency department generally does not qualify as a hospitalization, unless the event qualified as an SAE based on other criteria.
  - Results in persistent or significant disability/incapacity
  - Considered medically significant by the investigator or requires intervention to prevent any of the outcomes above. Medically significant are those events considered important in the investigator's opinion and which may not be immediately life-threatening or result in death or hospitalization but may jeopardize the subject or may require intervention to prevent one of the outcomes listed in the definition above.

b. Reporting of Adverse Events (AE)

The Investigator and/or research coordinator at each participating center will be responsible for collecting data in regard to adverse events. The investigator must decide whether each incident meets the definition of a SAE.

*Reporting Requirement:* Once the local Principal Investigator (PI) determines that an adverse event meets the IRBs' reporting requirements, he/she must report the SAE and related safety information to the Coordinating Center on the required *Significant Adverse Event Report Form* (See form attached) provided for this purpose. Supporting documents, including a copy of the Informed Consent, should also be emailed/submitted through REDCap. For reasons of confidentiality, subject's names must not be included in the report. Additionally, local SAEs must be reported to the IRB of record per policy. If the adverse event results in the need to revise the informed consent, or other study documents, the PI will submit a request for a modification through the Coordinating Center to the IRB of record.

c. Annual Data and Adverse Events Report

This report will be prepared annually by the PI and research coordinator at the Coordinating Center. This report will include the number of subjects actively enrolled, those that abandon and complete the research protocol, as well as, all side effects and adverse events in both groups.

In addition, an interim analysis or treatment monitoring will be performed by VCU Research Incubator. Due to a small risk related to RFA (estimated 2-3%), this interim analysis will be performed once the first 15 subjects (half of sample size) have completed a 15-month protocol. Data reports and interim analysis will be reviewed by the IRB at the Coordinating Center and DSMB during its convened meetings.

d. Data management and safety review

Collaborating centers and the Coordinating Center shall immediately notify each other, and the Coordinating Center shall promptly notify the IRB, upon identifying any aspect of the Protocol, including unanticipated problems involving risk and information discovered during site monitoring visits/remote monitoring visits or in the study results that may adversely affect the safety, well-being, or medical care of subjects, or that may affect the willingness of subjects to continue participation in the research, may influence the conduct of the study, or may alter the IRB's approval to continue the study. When subject safety could be directly affected by study results, the Coordinating Center will notify participating sites who will provide written communication to affected subjects.

A Data and Safety Monitoring Board (DSMB) will consist of 2 heart failure specialists (Drs. [name] and [name]) and a cardiac electrophysiologist ([name]) (see letters of support) that have no direct investment in the study to prevent jeopardizing subject safety. In addition to the IRB, the DSMB will review the research protocol and plans for data safety and monitoring, evaluate the progress of the trial with periodic assessments of data quality and timeliness, participant recruitment, accrual and retention, participant risk versus benefit, and reports from related studies.

The DSMB will meet every 4 months to review data and adverse event reports. Additionally, they will meet to review interim analysis when available. This will be performed in a closed session with open access to the PI if requested by the Board. Data monitoring will focus on several areas: 1) Performance, which will allow us to assess site performance with respect to subject recruitment, retention and follow-up, flow of data forms, protocol adherence and quality of data; 2) Safety, which allows us to assess the magnitude of adverse events; and 3) Treatment, in order to monitor and assess treatment effects.

The DSMB has the responsibility to make written reports of their findings and recommendations to the Coordinating Center, IRB, NIH/NHLBI (funding institution) and investigators concerning continuation or conclusion of the trial if it considers that RFA has a significantly higher benefit or increased risk as compared to the control arm. Annual data safety, adverse event reports and interim analyses may result in the need to revise the informed consent, or other study documents, for which the PI must submit a study amendment to the IRB. This could result in early study termination only if continuation will not produce benefit to subjects or if the treatment outcome is known to have benefit.

In accordance with the terms of the Federal Wide Assurance, the Office for Human Research Protections (OHRP) and the Federal Drug Administration (FDA) will be notified in a timely manner of 1) serious or continuing noncompliance; 2) significant adverse events involving risk to participants or others; or 3) suspension or termination of IRB approval for a study.

Governance plan, administrative, technical and scientific responsibilities of PIs and research coordinators are detailed in the document: Leadership plan. If an unexpected scenario was to occur, all PIs will have to be in agreement in order to change or deviate from the protocol with appropriate notification to collaborating centers. Similarly, if during a review or recommendation of the Data Safety Monitor Board (DSMB) is made, all PIs will discuss and agree to modify or make appropriate changes to address concerns of the DSMB.

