- 2) The rate of responders (defined as improvement of LVEF  $\geq$  10% points) with HF medical therapy alone during observation period will be less than 15% *in subjects with CM associated with frequent PVCs*. In contrast to HF medical therapy alone, RFA and AADs will have a responder rate of *at least 35% in the same population*. *Furthermore, RFA will have a greater 1-year response rate when compared to AAD therapy.*
- 3) *RFA will have a lower rate of composite adverse events (worsening NYHA class, HF admission, treatment side effects & complications, and death), arrhythmia burden and a better long-term tolerance than AADs.*
- 4) The prevalence of CM (LVEF  $\leq$  45%) and frequent PVCs ( $\geq$ 10% burden) is largely under recognized in subjects undergoing ambulatory ECG Holters (Part II).

**Methods.** To test our hypotheses, we propose: 1) a clinical pilot study to prove the feasibility of a large-scale multicenter clinical trial (PAPS study) of subjects with probable PVC-CM, and 2) screen near 20,000 consecutive ambulatory ECG Holter monitors of all participating centers to identify all subjects with probable diagnosis of PVC-CM (PVC burden  $\geq$ 10% and LVEF  $\leq$ 45%). The clinical pilot study will enroll between 36-39 subjects with frequent PVCs (burden  $\geq$ 10%) and CM (LVEF  $\leq$ 45%) and randomize them to either: 1) RFA or 2) AADs. Prior to treatment, a baseline cardiac MR will be performed if clinically indicated and be allowed a 3-month observation period. To assess the effects of PVC suppression, we plan to compare changes in LV function, rate of responders (defined above), PVC burden/arrhythmias and clinical/functional status (QOL, HF symptoms and admissions, NYHA class) and adverse events between observation period both PVC suppression strategies (RFA or AAD).

To identify the best PVC suppression strategy, we will perform similar comparisons between RFA and AAD treatment groups during a 12-month follow up using a Prospective Randomized Open, Blinded End-point (PROBE) study design. The treatment regimens will be compared in an intention-to-treat analysis.

Our study is *unique due to its multidisciplinary approach and design* including: 1) observation/control period that allows us to assess for spontaneous improvement of PVCs and/or CM, and 2) active treatment to all subjects, which will allow for easier subject enrollment and retention with minimal drop out.

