**Table 2. Table of Study Procedures**

	3-month Observation			12-month Treatment Phase					
	Obs-V1 Baseline	Obs-V2 2-mo	Obs-V3 3-mo	Tx-V1 Baseline	Tx-V2 1-mo	Tx-V3 3-mo	Tx-V4 6mo	Tx-V5 9-mo*	Tx-V6 12-mo
Timeline in Weeks (range of days)	Week 0 (Day 0)	Week 9 (51-63)	Week 12 (84-96)	Week 12-15 (84-105)	Week 21 (141-153)	Week 26 (176-188)	Week 38 (260-272)	Week 50 (344-356)	Week 64 (441-454)
Informed consent	X								
Inclusion/Exclusion Criteria	X								
Collection of demographic data	X								
Medical History	X								
Physical Exam	X		X		X	X	X	X	X
Functional status/NYHA class	X		X		X	X	X	X	X
QOL Minnesota HF Questionnaire	X		X		X	X	X	X	X
Current / change of medications	X		X		X	X	X	X	X
12-lead ECG	X*	X*	X		X*	X*	X*	X*	X*
Ziopatch	X	X ‡			X €	X	X		X
Echo	X £		X ‡			X	X*		X
BNP / ProBNP levels ESR & CRP	X* £		X*		X*	X*	X*	X*	X*
Urine pregnancy test (if applicable)	X		X	X	X	X	X	X	X
CMR	X*								
TSH (if assigned to amiodarone)			X				X		X
LFT (AST) (if assigned to amiodarone)			X				X		X
Treatment randomization	X								
Initiation of RFA or ADD				X					

Collection of unsolicited AEs	From Obs-Visit 1 until Tx-Visit 6
--------------------------------------	-----------------------------------

Footnote: \*, visit/intervention if clinically indicated.

‡ LVEF results of 2D-echocardiogram and Ziopatch have to be available at the time of Observation Visit 3 (Obs-V3). € If PVC burden >10%, subject should be considered to either adjust antiarrhythmic therapy (AAD group) or second ablation procedure (RFA group) based on their randomization group. ESR, Erythrocyte sedimentation rate; CRP, C-reactive protein. £ Must be done within 150 days of Enrollment Visit (Day 0)

Crossover between PVC suppression strategies is not encouraged. We request that crossover only be considered after 6 months of initiation of treatment, for which an intention-to-treat analysis will be performed. However, if crossover occurs before 6 months of initiation of treatment, subjects will be withdrawn from the study and included in the PVC-CM registry if the subject provided consent.

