iii. *Observation – Visit 3.* Similar to Visit 1, appropriate data collection forms should be used to collect current medical therapy, NYHA functional class and Minnesota HF quality of life questionnaire (QOL). 12-lead ECG should be obtained if clinically indicated. Transthoracic echocardiogram should be performed to assess LVEF and a copy mailed to the Echo Core laboratory led by [name] III, M.D. The local PI and designated site staff will be able to log in to iRhythm's ZioReports to obtain the Zio Patch report that should include a 2-week PVC burden.

[figure not shown]
If PVC burden remains  $\geq 10\%$  and LVEF  $\leq 45\%$ , then the subject will either initiate antiarrhythmic drugs or undergo RFA procedure (see Section C: Description of the intervention/treatment) and will continue on protocol as scheduled. However, if these criteria are no longer met, the subject is considered a screen failure and is withdrawn from the study. In such a case, the treatment decision is solely at the discretion of the electrophysiologist caring for subject. Nevertheless, this subject will be included in a PVC-CM registry if consent was provided (described above Section A.1).

i) *Treatment – Visit 1.* This is considered the baseline visit where PVC suppression strategy assignment is initiated (either RFA or AADs). If the subject is randomized to RFA, we will request that sites complete the RFA data collection form which includes information during the RFA procedure as well as recovery, complications and hospital stay. EPS will be performed on their baseline medications, except for antiarrhythmic drugs class II (beta blockers) which will be held at least 5 half-lives prior to procedure. Beta blockers should be resumed after RFA.

iv. However, subjects randomized to AADs can have this visit combined with Observation-Visit 3. In addition, subjects in the antiarrhythmic (AAD group) will require a baseline TSH and LFTs (AST only) if amiodarone is chosen.

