A 2-week ambulatory ECG Holter (Zio Patch, IRhythm, Inc.) will be obtained 4-6 weeks after initiation of AAD to assess whether PVC suppression was successful (defined above). If successful PVC suppression is not achieved, we will ask sites to consider either an increase in the antiarrhythmic dose or change of antiarrhythmic as noted above. A repeat 2-week ambulatory Holter monitor will be done 4 weeks after adjustment of AAD to re-assess PVC suppression.

Radiofrequency Ablation (RFA) of PVCs. RFA will be performed after completion of 3-month observation period). EPS will be performed on their baseline medications, except for antiarrhythmic drugs class II (beta blockers) which will be held at least 5 half-lives prior to procedure. Beta blockers should be resumed after RFA.

EPS and RFA will be performed using standard techniques and protocols similar to those subjects that do not participate in this clinical study. Multipolar electrode diagnostic catheters will be inserted. If no ectopy is present at baseline, isoproterenol may be infused at rates up to 10mcg/min. If the ectopy is infrequent despite adrenergic stimulation, pace mapping will be performed at a pacing cycle length determined by coupling interval of the spontaneous ventricular ectopy. RV or LV PVCs will be mapped/ablated at the discretion of the electrophysiologist. Coronary angiography and/or intracardiac echo will be performed as needed. RFA will be performed at the site of earliest endocardial activation or best pace map. RFA applications will be delivered for at least 30 seconds if adequate power at the electrode-tissue interface is achieved. RFA will be continued for at least 60-120 seconds in sites where PVCs are abolished within 30 seconds. After ablation of the PVCs, isoproterenol will be administered at 2-10 mcg/min as required to shorten sinus CL to 500ms to confirm that PVCs are not inducible by adrenergic stimulation. In the event of polymorphic PVCs, all morphologies are to be targeted for ablation. Subjects will be observed overnight in a telemetry bed and discharged home the next day, as it is current standard of care.

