#### **E. Primary and secondary outcome measures.**

*The outcomes are divided in primary and secondary end-points (Table 3).*

*The primary end-points will consist of:*

1. *Improvement of LVEF after PVC suppression at 12-month follow-up.* This is chosen as primary-end point due to the known prognostic value of LVEF. The lower the LVEF, the higher the risk of sudden cardiac death and heart failure. This will compare the overall improvement or change in LVEF between RFA and AAD groups. This end-point will support that either RFA or AADs have an overall better outcome due to significant improvement of LV function with potential impact on morbidity and mortality associated with PVC-CM.

2. *Responders to PVC suppression strategy at 12-month follow-up* (See rationale under Section “Definitions” in 3rd paragraph of Aim 2). Assessment of the number of responders (delta LVEF  $\geq$  10%) after PVC suppression strategies (RFA or AADs) will assess the effectiveness of RFA and AADs to reverse or improve cardiomyopathy induced by frequent PVCs. Evidence that either RFA or AADs is superior to improve or even reverse LV dysfunction in subjects with high burden PVCs could have significant impact of morbidity and mortality including future heart failure and ventricular arrhythmias, and also may avoid ICD implantation.

*The secondary end-points will consist of:*

1. *Efficacy of RFA vs AADs groups to achieve successful PVC suppression at 12-month follow-up, defined as a reduction of PVC burden  $\geq$ 80% (regardless of LVEF change). Understanding the success rate of PVC suppression between RFA and AADs will help better determine the best treatment to those subjects with high PVC burden.*

2. *Composite end-point of adverse events at 12-month follow-up, including worsening in NYHA functional class (I-IV), number of HF and cardiac-related admissions, RFA complications and AAD adverse effects and cardiovascular death.*

This adverse event composite end-point is chosen to understand the overall complications and adverse effects/events related to RFA and AADs. Worsening of NYHA functional class will be defined as when/if the subject’s functional status worsens by one NYHA class. Hospital admissions will be defined as any visit to ED or hospital admissions related only to a cardiovascular event such as heart failure, angina, pre/syncope and palpitations.

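### Ablation subjects get a research-team check 1-2 weeks after treatment; drug-arm subjects have no scheduled adverse-event assessment before the first common visit

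*Combined protocol and SAP*

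**What the plan says.** The Data Safety Monitoring Plan sets early follow-up for one arm: "Those subjects randomized to the RFA group will be evaluated immediately, throughout the first 24 hours and 1-2 weeks after the procedure". The research team does this, and the plan describes it as usual post-procedure follow-up. Table 2 does not list these contacts.

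For both arms, Table 2 places treatment start (Tx-V1) at "Week 12-15 (84-105" days) and the next visit (Tx-V2) at "Week 21 (141-153" days), with nothing between them. Its adverse-event row reads "Collection of unsolicited AEs" and runs from enrolment to the last visit. Section B adds that "subjects randomized to AADs can have this visit combined with Observation-Visit 3". Section D says that a 2-week Holter "will be obtained 4-6 weeks after initiation of AAD to assess whether PVC suppression was successful", and gives the same interval after RFA.

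Secondary end-point 2 (Section E) is a composite that includes RFA complications and AAD adverse effects, with no severity threshold. Its stated purpose: "This adverse event composite end-point is chosen to understand the overall complications and adverse effects/events related to RFA and AADs". Hypothesis 3 in the Specific Aims predicts that "RFA will have a lower rate of composite adverse events". Section F says the pilot's adverse-event rates will help to design and power the large PAPS trial.

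**The concern.** A composite of harms compares fairly between arms only if both arms are asked about harms at similar times and in similar ways. Here one arm is seen by the research team 1-2 weeks after treatment, and the other is left to volunteer events until Tx-V2. The Data Safety Monitoring Plan says that all grades of toxicity are noted, so mild events are recorded, and these depend most on someone asking. An early drug effect that resolves within a few weeks may never be reported, or may be recalled imprecisely later, while an ablation event of similar grade would be found at the 1-2 week check. Two things are at stake: the between-arm comparison in hypothesis 3, and the early AAD event rate carried into the large trial. Blinded adjudication does not help, because the committee can act only on events that reach it.

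**Working it through.** **1. Time from treatment start to Tx-V2.** The plan implies a figure in two places: Table 2 heads Tx-V2 as the one-month visit, and Section D puts the Holter at 4-6 weeks, which is 28-42 days. The Table 2 day windows do not reproduce this:

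- shortest gap: 141 − 105 = 36 days (5.1 weeks)
- longest gap: 153 − 84 = 69 days (9.9 weeks)
- by week labels: 21 − 15 = 6 weeks to 21 − 12 = 9 weeks
- AAD started at Obs-V3 (days 84-96): 141 − 96 = 45 to 153 − 84 = 69 days

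The ranges 28-42 and 36-69 overlap only at 36-42 days. The heading, the day window and the Section D text must be reconciled; this review does not say which is right.

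**2. How far the RFA check precedes the first common assessment.** The check falls 7-14 days after the procedure.

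- against the Table 2 windows: 36 − 14 = 22 to 69 − 7 = 62 days earlier
- against the Section D Holter: 28 − 14 = 14 to 42 − 7 = 35 days earlier

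On either reading, the RFA check comes at least two weeks earlier.

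**3. Other planned contacts with AAD subjects before or around Tx-V2.**

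| Contact | Section | Described as an adverse-event assessment? |
|---|---|---|
| Holter, 4-6 weeks | D | No; tests PVC suppression, and RFA subjects have it too |
| Monthly emails or calls | Protection of Human Subjects | No; a retention measure for both arms |
| Monthly pregnancy test | A and J | No; women of childbearing age only |
| Instruction to call about unusual events | Data Safety Monitoring Plan | Passive, both arms |

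None is the counterpart of the RFA 1-2 week check.

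**4. Size, as an illustration only.** The documents give neither an early-event rate nor a detection rate. Assume 19 subjects per arm, the same true early-event rate *p* in both arms, and AAD detection at a fraction *s* of RFA detection. The spurious difference is *p*(1 − *s*), and the AAD events missed are 19*p*(1 − *s*).

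| p | s = 0.75 | s = 0.50 |
|---|---|---|
| 10% | 2.5 points, 0.5 events | 5 points, 1.0 event |
| 20% | 5 points, 1.0 event | 10 points, 1.9 events |
| 30% | 7.5 points, 1.4 events | 15 points, 2.9 events |

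These figures apply to the early-harm component. A subject already counted in the composite for another reason does not change it, so the effect on the composite is no larger and probably smaller.

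**The case against.** Several points on the other side stand.

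- **Contact does exist.** A reader of Table 2 might infer that AAD subjects have no scheduled contact for 5-10 weeks. The documents do not support that: the Holter, the monthly emails or calls, and the pregnancy tests in a subset are all planned. What is missing is a scheduled adverse-event assessment. The wait until Tx-V2 also applies to both arms; only the RFA-specific checks differ.
- **Most of the RFA contact is inherent to the procedure.** It is tempting to count three RFA assessments against none. The immediate and 24-hour checks belong to the procedure and the overnight telemetry stay, and have no natural drug counterpart. The imbalance that can be removed is the one check at 1-2 weeks.
- **General capture covers both arms.** Section C requires all events to be documented throughout, and the Data Safety Monitoring Plan monitors adverse events in everyone. Tx-V2 also records medication changes, so a drug effect that led to a change leaves a trace that prompts enquiry. This narrows the concern to mild, self-limited effects. It does not offset an additional active check in one arm.
- **Net direction is open.** A reader might infer that the 12-month comparison is biased against RFA and the overall AAD rate too low. The documents do not support that either. Subjects on amiodarone have thyroid and liver tests at Obs-V3, Tx-V4 and Tx-V6, and lung and eye examinations are to be considered, which raises detection of late drug effects.
- **The setting is modest.** This is a secondary end-point in a pilot of 36-39 subjects, and the Data Sharing Plan says the pilot data are not meant to settle the benefits of the strategies. The early imbalance taken alone would work against hypothesis 3. But the pilot's product is a set of rates for planning, and a distorted rate does harm whichever hypothesis it favours.

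**Conclusion.** The concern holds in limited form. RFA subjects have a scheduled research-team assessment at 1-2 weeks, and AAD subjects have no scheduled adverse-event assessment before Tx-V2. The difference in timing is 22-62 days by the Table 2 windows or 14-35 days by the Holter interval. The consequence is a risk, not a certainty, that early mild or self-limited AAD effects are under-counted relative to early RFA events in secondary end-point 2. Deaths and admissions depend little on visit timing. The net direction over 12 months cannot be determined from the documents. The range of 2.5 to 15 points (about 0.5 to 3 of 19 subjects) rests wholly on assumed event and detection rates and should not be read as an estimate. The matter merits a change because events never elicited may not be recoverable at analysis and the remedy is cheap.

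**What to change.** 1. Add to Table 2 one scheduled adverse-event contact 1-2 weeks after treatment start in both arms, using the same adverse-event form and the same questions. For RFA this is the existing 1-2 week assessment, now listed. For AAD it is a telephone call, which can be timed with a monthly retention contact already planned.
2. In Section I, report events found only at the immediate and 24-hour post-procedure checks, or only by arm-specific monitoring such as the amiodarone laboratory tests, on a separate line from events found at contacts common to both arms. The current Adverse Events form has no field for how an event came to light, so add one.
3. Reconcile the Tx-V2 heading and day window in Table 2 with the 4-6 week interval in Section D.

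The cost is about 19-20 short calls by existing coordinators over the whole trial, one Table 2 row, one form field and one reporting line. No treatment changes.
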